4.2. Qualitative Analysis

Interviews and focus groups will be taped and transcribed *verbatim*. Data will be managed using specialist software for qualitative data (NVIVO). The data will be analysed using the principles of Framework analysis (Ritchie & Spencer, 1994). There are five key stages in the analysis: 1) *Familiarisation* – the transcripts will be read thoroughly by all researchers to identify key themes. 2) *Developing a thematic framework* - a framework was developed that was applied to the transcripts. Following discussions with co-researchers, this framework will then be expanded and refined. 3) *Indexing* – themes and emerging subthemes are labelled and indexed. 4) *Charting* – framework involves devising a series of thematic charts or matrices. 5) *Mapping and interpretation* – the aim is to bring out the key characteristics and map and interpret the data as a whole. A benefit of using Framework analysis is that strategies and recommendations for practice and policy may be elicited at this stage.

4.3. Outcome measures

The primary outcomes will be live birth and twin births. An important consideration in the modelling is the appropriate aggregated outcome measure, or measures, for a course of treatment. The live births per cycle started, egg collection or transfer cycle whilst convenient, are not appropriate measures by which to compare treatment scenarios which may involve multiple cycles. Part of the qualitative work proposed is to identify appropriate aggregated outcome measures which encompass the patient, clinical and societal perspectives of successful treatment.

5. Project Governance and Ethics

5.1. Ethical arrangements

Approval from an NHS Research Ethics Committee will be sought through the COREC system once funding is confirmed, and before the project commences. All the data are available from routine clinic or HFEA records, and there is no need to contact individual patients. All data will be anonymised on extraction and provided to the researchers without any personal identifiers. As such we believe it is unnecessary, as well as impractical to seek individual patient consent, and indeed it would probably be considered unethical to re-contact patients unnecessarily. We have obtained ethics approval to analyse the Manchester data on this basis. The qualitative work will involve patients, and written informed consent will be obtained. This work has the potential to raise distressing topics and provoke conflict. We will work closely with the subfertility counsellors to minimise and mitigate such events, and the interviewer has the necessary experience and training to deal with such issues as may arise.

5.2. Research Governance

Research governance will be overseen by the University of Manchester. PS120906

5.2.1. Management Group

The project will be managed by a Management Group comprising the named investigators, the RA statistician, the Study Nurse involved in recruitment and the qualitative research assistant. This will meet monthly to oversee the project.

5.2.2. Advisory Group

In addition we will create an Advisory Group (AG) drawn from the wider collaborators and including a patient representative. The AG will meet at the start of the project to approve the protocol and at approximately 6 month intervals to provide guidance and a wider clinical perspective. See appendix 5 for membership. This group will be chaired initially by the Chief Investigator, but may elect its own chair at the first meeting. The format of the meetings will be agreed by the Group at the first meeting. The first meeting will be face-to-face and will provide an opportunity to meet the research team.

5.2.3. Contracts

The investigators all have contracts with both the University and the Central Manchester Trust and similar arrangements will be made for all those working on the project.

5.2.4. Publication

All manuscripts and conference presentations must be approved by the Management Group before submission. Authorship will be determined by that group following the Vancouver Group guidelines (www.icmje.org) Specifically we note:

- Authorship credit should be based on 1) substantial contributions to conception and design, or acquisition of data, or analysis and interpretation of data; 2) drafting the article or revising it critically for important intellectual content; and 3) final approval of the version to be published. Authors should meet conditions 1, 2, and 3.
- Acquisition of funding, collection of data, or general supervision of the research

group, alone, does not justify authorship.

All collaborators contributing data will be acknowledged by name and affiliation in all publications that use that data, and contributors will have the chance to review the manuscript before submission.

Unless otherwise indicated (e.g. for methodological or other sub-studies) the default is that all 5 investigators and the RA will be listed as authors of all publications together with anyone else who has made a significant intellectual input to the manuscript.

The primary publication will be the HTA monograph which will be authored by the named investigators and the RA and reviewed by the SAG.

6. Project timetable and milestones

We propose a 4-month lead in time from confirmation of funding to the formal project start. During this time we will obtain ethical and Trust R&D approvals and appoint the Research Associate. We anticipate that this will lead to a start date of 1/1/07, but this could be earlier or later if required by the contractual process. The project is then expected to last for 2 years.

	Year 1				Year 2			
	Q1	Q2	Q3	Q4	Q5	Q6	Q7	Q8
Literature review	x	x	x	x				
Collate and clean datasets	x	x						
Preliminary analyses			x					
Logistic modelling			x	x				
EU modelling				x	x			
Scenario modelling					x	x	x	
Patient/clinician perspectives	x	x	x	x				
Analysis of qualitative data			x	x	x	x		
Patient consultations			x	x	x	x	x	x
Write up								x

Key milestones:

Project start: Ethical approval obtained and Research Associate in post

6 months: Single centre datasets collated and validated

12 months: Patient interview work on perspectives completed

12 months: Logistic modelling of SET & DET cohorts

15 months: EU modelling of single-centre data

18 months: Patient/clinician perspectives analysis complete

Appendix III Interview Topic Guide

LREC reference number: 06/Q1403/255

Interview Group Topic Guide v1.1 (04/05/2007)

INTERVIEW GUIDE

General introduction

As we explained in our letter current UK policy limits the number of embryos transferred to two, but many doctors advocate single embryo transfer, due to the increased risks of twin pregnancies. It is clear to us that couples undergoing IVF treatment may not share the same perspective on the risk and benefits as doctors, and we wish to understand what patients feel so that the results of our research will reflect your wishes. We are conducting this interview study to attempt to understand patients' perspectives on the choices you and your doctor have to make. This interview will be taped with your permission.

Short demographics questions:

How old are you?

How old is your partner?

Do you have any children in your family?

How long have you been seeking treatment for infertility?

How is your treatment going to be funded?

TOPIC AREAS TO BE DISCUSSED:

➤ **Could you describe to me your general experience of treatment to date?**

Ascertain stage of treatment

Length of time on waiting list

Number of treatments to date

General experiences of treatment – explore the perceptions of a 'good' outcome?

➤ **Discuss differences between SET and DET, and explore current knowledge regarding treatment:**

Explore attitudes to twin pregnancy

Assess current understanding of risks associated with multiple births

Explore facilitators to eSET

Explore barriers to eSET

Discuss eSET policy

LREC reference number: 06/Q1403/255

- **We recognise that during your treatment you will have a number of important decisions to make. We would like to know how involved you would like to be with your doctor in making these decisions?**

Explore preferences for involvement in treatment decision making:

- medically led
- patient led
- collaborative model

Ascertain if the preferred model of decision-making should be different at the different treatment stages

- **Clearly, having clear and accurate information about the treatment process is essential. We would like to know what kind of information you would find most helpful?**

Explore information preferences:

Ascertain information needs at key treatment stages

- what kind of information is most helpful
- timing of information
- amount of information
- format of information

- **In medical research a common method of finding out which is the best form of treatment is to conduct a randomised controlled trial. Have you heard of this kind of research? (if not, explain briefly)**

Ascertain current understanding of randomised controlled trials

Explore views of being randomised to receive one or two embryos

- **Is there anything I have missed in our discussion that you consider to be important?**

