2.5. Patient perspectives (objectives 3 & 4)

In this phase of the study we will undertake in-depth qualitative interviews with couples who are in the process of undergoing IVF treatment. The aim is to explore the patient perspective of treatment choices as they travel through the treatment process. Therefore, interviews will take place at 3 key decision-making stages: a) waiting list; b) after the first information meeting and clinical appointment (pre-treatment) and c) after the second cycle of treatment. This latter group will allow for views to be assessed once the outcome of an initial treatment cycle is known and after the opportunity to reflect on the choices through a second treatment cycle. Approximately 5 to 10 couples per stage will be invited to take part in this study. Purposive sampling techniques will be employed to ensure maximum diversity of sample to include different female ages, parity, duration of infertility and source of funding (which is related to the number of treatment cycles which the couple receive). Couples will be invited to take part in this study, and once consent has been obtained, interviews will take place in the setting (clinic/home) of their choice.

Specifically we will plan:

- a. To assess couples' knowledge and views on embryo transfer and twin birth prior to treatment, after counselling and post-treatment.
- b. To explore the potential facilitators and barriers to eSET.
- c. Evaluate the patient perspectives on the decision-making process during key stages of the treatment journey, including consideration of measures of success and attitudes to twin births.
- d. Determine the level of involvement couples would prefer in the decision making process regarding treatment choices.
- e. To establish at what stage (pre-treatment) information regarding treatment choices about eSET should be presented, and in what format.
- f. To explore couples attitudes to research, in particular, their understandings of randomisation.

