3.2.2. Interview Conduct

In-depth exploratory interviews, employing the conversational style, will be conducted with couples at the three key treatment stages of interest (waiting list; after the first information meeting and clinical appointment; and after the second cycle of treatment). Interviews will be conducted in a setting of the couple's choice (either home or clinic). Travel expenses and refreshments will be provided for those couples who opt for a clinic setting. All interviews will be taped, with permission, and transcribed prior to analysis.

The interview will begin by asking couples to describe their individual experiences, including their interactions with the health care system. In effect, the couples will be asked to tell their "stories". Should topics not emerge that are relevant to the study the interviewer ([name]) will refer to the interview schedule (Appendix 3) and guide the respondents accordingly. In keeping with qualitative research the interviews will be analysed in stages. Early interviews will be analysed and the data used to inform the format of later interviews. So when couples introduce information/areas which are new (i.e. not recorded in the literature or previously known to the researcher) these will be incorporated in to later interviews.

All interviews will be coded by number and anonymised. All interviews will be transcribed verbatim by secretarial staff who are used to dealing with material of a medical/research nature.

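### The interview guide tells couples that twin pregnancies carry increased risks, and that many doctors therefore favour SET, before it asks what they understand of those risks, so unprompted awareness cannot be cleanly elicited

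*Protocol*

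**What the plan says.** Aim (a) in Section 2.5 is to assess couples' "knowledge and views on embryo transfer and twin birth prior to treatment, after counselling and post-treatment". The interviews fall at three stages: on the waiting list, after the first information meeting and clinical appointment, and after the second treatment cycle. On numbers, the section says "Approximately 5 to 10 couples per stage will be invited to take part in this study".

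Appendix III gives the interview guide. Its general introduction begins "As we explained in our letter current UK policy limits the number of embryos transferred to two" and continues, in the same sentence, that "many doctors advocate single embryo transfer, due to the increased risks of twin pregnancies". The next sentence says that "couples undergoing IVF treatment may not share the same perspective on the risk and benefits as doctors" and that the team wishes to learn what patients feel. Demographic questions and an open question about treatment experience follow. The second topic area then covers SET and DET, with the prompts "Explore attitudes to twin pregnancy" and "Assess current understanding of risks associated with multiple births".

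Section 3.2.2 describes a conversational style: "The interview will begin by asking couples to describe their individual experiences", with the schedule used for topics that do not come up unaided. Under Section 3.2.1, couples at all three stages receive an invitation letter and an information sheet beforehand.

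**The concern.** A question about what someone currently understands is informative only if the interviewer has not just supplied part of the answer. Here the study states the headline fact, that twin pregnancy carries added risk, and the professional position that follows from it, before either topic is raised with the couple. After that, an interviewer who hears a couple say that twins are riskier cannot tell whether they knew this or are repeating what they were told.

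The waiting-list couples have most to lose. They are the only group interviewed before the first information meeting and clinical appointment, so they are the best source for what couples bring with them. If the study itself tells them about the risk, their starting point on that item is no longer observed. Attitudes could also be affected, since hearing what doctors advocate may cue deference on a question where, according to Section 1.1, patients and clinicians differ.

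**Working it through.** No arithmetic bears on the substance. The check is to set the order of the guide against the aim it serves.

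1. **Order of delivery (Appendix III).** The introduction, with the risk statement and the doctors' position, comes first. Demographics come second and treatment experience third. Attitudes to twins, understanding of multiple-birth risk, and facilitators and barriers to eSET come fourth. The disclosure precedes both relevant prompts.

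2. **Earlier exposure.** The introduction ties its opening sentence to the letter. The letter is not among the documents, and the phrase could cover only the two-embryo limit or the whole sentence. On the natural reading, the risk message has reached couples before the interview starts. The information sheet, which Section 3.2.1 says explains the study's rationale, may carry it too.

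3. **Against aim (a).** The aim asks for knowledge as well as views, and includes the period before treatment. For knowledge, the disclosure gives away that twin risk is increased. It does not say which risks, how large, or whether to mother or child, so the detail behind the headline can still be explored. For views, the disclosure is a cue, partly offset by the sentence acknowledging that couples may see things differently.

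4. **Can the couples' own stories serve as an unprompted record?** Section 3.2.2 has them come before the schedule is used, which helps. They still follow the letter and, in the order of Appendix III, the introduction. No step in the plan records understanding before the statement is made.

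5. **How the same guide treats another topic.** For randomised trials, Appendix III asks whether the couple has heard of the method and explains it only if they have not. That is ask first, then explain. The twin-risk topic runs the other way.

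6. **Reach.** 3 stages × 5 to 10 couples = 15 to 30 couples invited, of whom 5 to 10 are at the waiting-list stage. This counts the interviews exposed to the wording. It does not measure a bias.

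**The case against.** The best defence is that this is exploratory work, not a survey. The interviews are conversational, couples speak first, early interviews shape later ones, and the data go to Framework analysis (Section 4.2). No knowledge score and no quantitative comparison between stages is planned. The introduction openly invites couples to disagree with doctors. Section 1.1 reports that patients' perception of twins is hard to shift and cites a study in which additional information left attitudes to a hypothetical eSET policy unchanged. Consent also requires that couples be told what the study is about.

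Most of this stands as far as attitudes are concerned, and it makes an effect there uncertain. It does not answer the point about knowledge: inviting disagreement does not withdraw a stated fact, and the cited study concerned attitudes. The consent argument limits how far priming can be removed, but stating the topic does not require announcing the risk and the doctors' preference first.

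Three stronger readings are tempting and are not supported:

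- A reader might infer that knowledge will appear higher and stage differences smaller than they are. That is plausible, but neither direction nor size can be established from the documents.
- A reader might infer that aim (e), on when and how to present eSET information, is undermined because it depends on differences in knowledge between stages. The Protocol does not say so, and the guide serves that aim with direct questions on the kind, timing, amount and format of information wanted.
- A reader might infer that the guide requires SET and DET to be explained before knowledge is explored. The heading joins discussion and exploration in one topic, and the items beneath it are prompts with no fixed order.

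**Conclusion.** The point holds in a limited form. The guide, and on its own wording the letter, discloses that twin pregnancy carries increased risk and that many doctors therefore advocate SET before understanding of that risk is assessed. Unprompted awareness under aim (a) cannot be cleanly elicited, above all in the waiting-list group. An effect on attitudes is possible but less certain. Knowledge of specific risks remains open to exploration.

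It is a minor matter. It concerns one item in the qualitative work and leaves the cohort data, the models and the primary outcomes untouched. The size of any distortion is unknown.

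The conclusion assumes that the introduction is delivered as scripted and, for exposure before the interview, that the unseen letter carries the risk message. Waiting-list couples may also not be wholly uninformed in any case, since Section 3.2.1 describes a waiting-list meeting at which basic treatment information is given.

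**What to change.** Reword the introduction neutrally, for example: we would like to understand how couples think about the number of embryos transferred. Make the same change in the invitation letter and information sheet as far as informed consent allows; changing the guide alone would leave the earlier exposure in place.

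Ask about attitudes to twins and understanding of multiple-birth risk before stating UK policy or doctors' views, following the ask-then-explain order already used for randomised trials. In the analysis, acknowledge any disclosure that remains, including for couples who have already received the existing letter, and do not present their awareness of twin risk as unprompted.

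The cost is small: wording and order changes with an ethics notification, and no extra interviews. Some priming from the consent material may persist, because couples must be told what the study is about.

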Appendix IV Focus group topic guide**FOCUS GROUP TOPIC GUIDE****TOPIC AREAS TO BE DISCUSSED:**

- **Open with a general discussion about the various treatment options e.g.**
 - Single embryo transfer (SET) – 1 cycle*
 - Double embryo transfer (DET) – 1 cycle*
 - SET with fresh embryo – 1 cycle*
 - SET with frozen embryo 1 cycle*
 - SET with one fresh & one frozen embryo – 2 cycle*

- **Present a selection of scenarios from the results of the statistical modelling:**

Provide instructions to the group (*via a Powerpoint slide*). This will cover:

 - What the terms mean*
 - How to read the scenarios*
 - How to rate the scenarios*
 - How long they have got to read and rate the scenarios*
 - Any questions before we begin?*

- **Explore general views, opinions and attitudes to the various scenarios presented:**
 - Did you find the exercise easy to do?*
 - Was this a useful exercise?*
 - Did any of you change your mind about a treatment after reading these scenarios?*
 - How do you feel about a policy that encourages SET?*
 - Is this different to how you felt before?*
 - What would be your preferred treatment option?*
 - What do you think is a 'good' treatment outcome?*

- **Discuss the concept of randomised controlled trials**
 - What is your understanding of randomised controlled trials?*
 - How you would feel about being 'randomised' to receive either one or two embryos?*
 - If you were invited to take part in such a trial would you agree to participate?*

- **Is there anything I have missed in our discussion that you consider to be important?**

